1.3 Rationale for the RA-308 Excimer Laser System

The RA-308 Excimer Laser system may cross calcified lesions without subluminal penetration, common when using the standard guide wire approach. Additionally, the energy delivered within the patient with the excimer laser is much lower than when using mechanical surgical methods. This may result in less vascular trauma and may improve the clinical outcome for the patient.

1.4 Previous Clinical Experience

The RA-308 Excimer Laser System and DABRA Catheter have been used on three patients to date. Their peripheral vascular blockages were ablated (crossed) and the patients were then treated with balloon angioplasty. There were no adverse events and the procedural outcomes were excellent.

1.5 Risk Analysis

We believe that the procedure does not pose a significant risk to the patient. The patients are likely candidates for amputation. In addition, the procedure does not pose additional risk to the patient because of the following:

- The endovascular procedure will occur anyway, regardless of whether or not the laser is used. This endovascular procedure is used to help diagnose the precise nature of the disease, the location of any stenosis, and treatment will be initiated with common endovascular tools, such as guidewires and balloons. The DABRA laser catheter will be attempted only after these tools fail or if the physician determines that there is no other option.
- The catheter does not present a potential for serious risk to the health, safety, or welfare of the subject, because they already have a high probability of amputation. In addition, the potential adverse events related to the DABRA catheter have low risk to these patients. Perforation is easily mitigated and repaired with a tamponade technique, and embolism or debris from any of these procedures is likely to be filtered downstream by the narrowing of the vasculature.
- The catheter is not implanted, and is not of substantial importance in treating the disease. It only crosses the lesion to allow therapeutic treatment. It is a small part of a much more complicated procedure. The energy delivered by the DABRA catheter is orders of magnitude less than other technologies, including mechanical, barometric, radiofrequency, and ultrasonic or sonic.
- All endovascular interventionalists have the skill and training to use this device safely. Excimer lasers have been used for over 20 years, and their operation is no more difficult than using a stand alone guide wire. The only difference is depressing the footswitch.

2.0 STUDY OVERVIEW

2.1 Study Design

The study is a multi center, prospective, non-randomized, open-label study conducted at two investigational centers in the US, one in southern Mississippi and one in southern California, with at least two operators at each site. 50 subjects can be enrolled. Follow-up

occurs at the end of the procedure in the form of an angiogram to determine if the lesion was crossed. Additional follow-up may not necessary because of the binary nature of the crossing, and also because any future follow-up would be assessing the effectiveness of adjunct therapy, e.g. balloon angioplasty. Long term results are entirely dependent on this subsequent treatment. Because the DABRA crosser only allows adjunct devices to be used, 30-day follow-up measuring the performance of the adjunct therapy might affect the physician's choice of therapy, and compromise the patient's treatment. Therefore, 30-day follow-up, which evaluates the effectiveness of the adjunct therapy, might raise ethical concerns.

However, the follow-up can be done by ABI, Doppler ultrasound, auscultation, or by discussion of the level of claudication and motion pain with the patient.

2.2 Study Objectives

To evaluate the safety and efficacy of the RA-308 Excimer Laser System and DABRA Catheter for treating subjects with symptomatic infrainguinal lower extremity vascular disease with chronic total occlusions that cannot be crossed with standard guide wires, or lesions where an attempt to cross would, in the opinion of the interventionalist, result in either a subintimal path or a perforation.

2.2.1 Outcome Measures

Procedural success, defined as crossing the target lesion based on angiographic analysis. Crossing the target lesion is defined as successfully placing any endovascular device distal to the occlusion.

No device related major adverse events

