3.2 Inclusion Criteria

Subjects must satisfy the following criteria before entering the study:

- Signed informed consent obtained.
- Symptomatic infrainguinal lower extremity occlusive vascular disease (Rutherford category 3, 4, 5 or 6), stable for at least 2 weeks prior to study inclusion.
- Lesions in the superficial femoral artery (SFA), popliteal, or infrapopliteal arteries
- At least one angiographically identifiable infrageniculate artery
- Patients must be poor surgical candidates, indicated by at least one of the following conditions:
 - Absence of venous autologous grafts (that is, lack of a suitable vein to use for bypass)
 - Poor (diffusely diseased or ≤ 1 mm diameter) or no distal vessels available for graft anastomosis
 - High risk of surgical mortality, evidenced by American Society of Anesthesiologists Physical Class 4 or higher
- Have a lesion that is a chronic total occlusion that cannot be crossed with a standard guidewire. NOTE: This can only be determined at the time of the procedure.

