4.2 Excimer Laser for Use in Plaque Photoablation

Refer to the device Instructions for Use for a thorough description of the procedure.

Procedure Description

The excimer laser crossing procedure is performed in the Catheter Laboratory using standard endovascular techniques. Following introduction to the vascular system and diagnosis using fluoroscopy, including determining that a standard guidewire cannot cross the lesion, the following general guidelines are followed:

1. Insert a commercial guide wire to the blockage.
2. Pass an appropriate guiding catheter (support catheter) over the wire to the lesion. (Steps 1 & 2 can be reversed depending on physician choice.)
3. Remove the guide wire if one fails to cross the CTO or if, at the physician's discretion, angiographic factors determine that a guide wire should not be used because of the presence of a rounded or eccentric stump might bias the guide to a subintimal route, or other complicating factor.
4. Save the initial guide wire and insert the laser catheter and perform a stepwise crossing of the lesion.
5. Cross the CTO with the laser catheter following the step-by-step procedure in the instructions for use.
6. Exchange the laser catheter with the previous wire or another wire.
7. Remove the guide catheter leaving the guide wire in place and, at the physician's discretion, insert other endovascular devices to enhance blood flow.

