6.0 STATISTICAL METHODS

6.1 Primary Objective

The primary objective of this study is to demonstrate that the Ra device meets its performance goal of a success rate in crossing vascular lesions of at least 65%. A study of the predicate device observed 37 successes in a trial of 47 patients, or a 79% success rate with a 95% confidence interval of 65-88% (Wilson score interval). The performance goal for the Ra device is thus set to be a success rate of at least 65% and the primary objective is to show that the Ra device exceeds this performance goal in a single-arm multi-site pivotal trial. Crossing success rate will be a binary endpoint, where successful crossing of a lesion is defined as crossing the target lesion based on angiographic analysis.

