6.3 Hypothesis

The following null hypothesis will be tested with an overall significance level of 0.025

$$H_0: p \leq 65\%$$

where p is the Ra device crossing success rate. The alternative hypothesis is:

$$H_a: p > 65\%$$

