11.0 MONITORING RESPONSIBILITIES

Ra Medical Systems, Inc. will serve as the sponsor of this clinical investigation. It is the responsibility of Ra Medical as the sponsor of the study to ensure proper monitoring of the investigation and to see that all the clinical requirements are met.

The procedural success determination is crossing the lesion that could not be crossed with a standard guide wire, and therefore not subject to bias. The procedural success is determined using fluoroscopic angiography and is not subject to bias, interpretation, or quantification,

because the lesion is either crossed or not crossed. Because of these facts, third party involvement in determining procedural success would have no added value and provide no additional verification. The placebo effect also need not be considered. It is not possible for the patient to affect the blockage during the procedure.

All information and data sent to Ra Medical concerning subjects and their participation in this investigation will be considered confidential. Only authorized Ra Medical personnel, Ra Medical representatives, and regulatory agencies will have access to these confidential files. All data used in the analyses and reporting of this investigation will be coded without identifiable reference to the subject.

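### The definition of crossing credits any device distal to the occlusion, while the test concerns the Ra device's own crossing rate, and no rule scores a failed laser attempt that another tool completes

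*Combined protocol and SAP*

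**What the plan says.** **Endpoint.** The synopsis and section 2.2.1 define procedural success as angiographic crossing of the target lesion and make that operational with one sentence: "Crossing the target lesion is defined as successfully placing any endovascular device distal to the occlusion". The laser is not named. Section 6.1 says only that "successful crossing of a lesion is defined as crossing the target lesion based on angiographic analysis", again without naming a device.

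**Parameter tested.** Section 6.3 sets the null hypothesis at 65% or less, "where p is the Ra device crossing success rate".

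**Decision rules.** Section 6.2 specifies a one-sided exact binomial test at 0.025. Section 6.5 gives two cut-offs, at least 13 of 14 or at least 40 of 50, and plans on a true rate of 97%.

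**Order of tools.**
- Section 1.5: "The DABRA laser catheter will be attempted only after these tools fail or if the physician determines that there is no other option".
- Section 3.2 requires that subjects "Have a lesion that is a chronic total occlusion that cannot be crossed with a standard guidewire".
- Section 4.2, step 5: "Cross the CTO with the laser catheter following the step-by-step procedure in the instructions for use". Step 6 exchanges the laser catheter for a wire, and step 7 permits other devices.
- Section 11.0: "The procedural success determination is crossing the lesion that could not be crossed with a standard guide wire".

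**Source of the goal.** Section 6.1: "A study of the predicate device observed 37 successes in a trial of 47 patients". How that study defined a crossing is not stated.

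**The concern.** Take a patient in whom the laser catheter fails and a different tool then passes the occlusion. Under section 2.2.1 the patient is a success, because a device lies distal to the occlusion. Under section 6.3 the patient is not a crossing by the Ra device. The plan does not say which governs.

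The eligibility rule narrows this situation but does not exclude it:
- Section 3.2 concerns a standard guidewire only. It does not cover a non-standard crossing tool, or a wire that passes later through a partly lased channel.
- Section 2.2 and step 3 of section 4.2 allow the laser without a failed wire attempt, at the physician's judgement. In those patients a later wire crossing is not ruled out by an earlier failure.
- Section 4.2 describes only the path on which the laser succeeds.

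The end-of-procedure angiogram in section 2.1 shows whether the lesion was crossed, but not by itself which tool did it. Section 11.0 treats the determination as free of interpretation and sees no value in third-party assessment, so any attribution would fall to the open-label operator without a written rule.

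What is at stake is the meaning of the primary result. The exact test holds its level for the outcome as worded. It need not do so for the laser's own rate, because the literal count is always equal to or higher than the laser-only count.

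**Working it through.** **Inputs from the plan.** Goal 65% (6.1); one-sided exact binomial test at 0.025 (6.2); cut-offs 13/14 and 40/50, planning rate 97% (6.5).

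**Step 1: reproduce the plan's figures.** With X binomial(n, p), the chance of meeting the goal is P(X ≥ cut-off).
- n = 14, at least 13: 0.0205 at p = 0.65; 0.9355 at p = 0.97 (stated 94%).
- n = 50, at least 40: 0.0160 at p = 0.65; above 0.9999 at p = 0.97 (stated 99.99%).

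Both agree. The sample-size arithmetic is not in question.

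**Step 2: one disputed patient, with no assumption about frequency.** Exact tail probabilities against 0.65:

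| Laser crossings | p | With one credited rescue | p |
|---|---|---|---|
| 39/50 | 0.034 (misses) | 40/50 | 0.016 (meets) |
| 12/14 | 0.084 (misses) | 13/14 | 0.021 (meets) |

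**Step 3: long-run effect.** Let p be the laser's own crossing rate and r the share of laser failures later crossed by another tool and counted. The documents do not give r, so it is an assumption. The scored rate is

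q = p + (1 − p) × r.

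The chance of meeting the goal equals 0.025 at q = 0.6628 for 40/50 and q = 0.6613 for 13/14. Solving r = (q − p)/(1 − p):
- p = 0.65: (0.6628 − 0.65)/0.35 = 3.7% for 40/50; (0.6613 − 0.65)/0.35 = 3.2% for 13/14.
- p = 0.60: (0.6628 − 0.60)/0.40 = 15.7%; (0.6613 − 0.60)/0.40 = 15.3%. In 50 patients, 15.7% is 50 × 0.40 × 0.157 = 3.1 rescued lesions out of 20 expected failures.

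Chance of declaring the goal met over a range of r:

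| True laser rate | r | 40/50 | 13/14 |
|---|---|---|---|
| 65% | 0 | 1.6% | 2.1% |
| 65% | 10% | 5.1% | 3.7% |
| 65% | 20% | 13.4% | 6.5% |
| 60% | 10% | 1.1% | 1.7% |
| 60% | 20% | 4.4% | 3.4% |

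**Step 4: at the planning rate.** With p = 0.97 and r = 25%, q = 0.97 + 0.03 × 0.25 = 0.9775. Expected successes in 50 rise from 48.5 to 48.9, and power with 14 patients rises from 93.6% to 96.1%. The effect is negligible there.

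**The case against.** The strongest reply is that the conflict appears only when section 2.2.1 is read alone. Section 6.3 names the Ra device. In section 4.2 the laser crosses, is withdrawn and is replaced by a wire, so a device lying distal to the occlusion is the natural confirmation that the laser's channel is usable. Section 1.5 likewise gives the catheter the role of crossing so that treatment can follow. Section 5.3 already collects a post-laser angiographic assessment and adjunctive procedures, which may allow attribution. The Instructions for Use and the content of the case report forms are not in the supplied text, so a scoring rule there cannot be excluded.

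Most of this stands. Laser-first crossing is the natural intent, and the absence of a rule is shown only for the visible text. But intent does not score a patient: section 4.2 has no branch for a laser failure, and nothing ties the section 5.3 data to the endpoint. A primary endpoint should also be complete in the protocol itself.

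The reply is also right that any disputed patient at any cut-off can tip a binary rule, so step 2 shows sensitivity and says nothing about how often rescue happens.

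A reader might go further and infer that rescue crossings will be counted, or that the trial's false-positive rate is inflated. The documents support neither. They give no rescue share, and with a true rate of 60% and r = 10% the chance of passing stays below 0.025 under both rules.

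**Conclusion.** The point holds as a mismatch between the operational definition (synopsis and 2.2.1) and the parameter tested (6.3). It goes beyond missing detail, because the rule as written, applied literally, gives the wrong score for the Ra device's rate when a laser attempt fails and another tool crosses. It should be fixed before enrolment.

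The size is conditional. One such patient is decisive only next to a cut-off. The long-run effect rests on the assumed r. It is greatest at the null boundary of 65%, needs r above about 15% at a true rate of 60%, and is negligible at 97%. It would be wrong to conclude that the sample size or cut-offs are in error, since both reproduce and neither needs to change.

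**What to change.** 1. In the synopsis, 2.2.1 and 6.1, define primary success as angiographically confirmed placement of an endovascular device distal to the occlusion through the channel made by the laser catheter. Score a lesion crossed only by a different tool or route after a failed laser attempt as not a Ra device success.
2. Before enrolment, assign one primary class, success or non-success, to a lesion that the laser opens partly and a wire finishes, so that the 13/14 or 40/50 count is defined. Report one sensitivity analysis with that class scored the other way.
3. Use the section 5.3 data for attribution and, if the case report form lacks it, add one item recording which device first passed distal to the occlusion.
4. Report the any-device rate as a secondary figure, because the predicate's crossing definition behind 37/47 is not given and comparability with the 65% goal is uncertain under either definition.

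**Cost.** Wording in three places and at most one form item; the observed success rate may be lower. The choice in item 2 affects power. Suppose a share s of the planned 97% is wire-finished (an assumption; s is not in the documents) and all of these are scored as non-successes, so that the rate is 0.97 × (1 − s):

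| s | Rate | Power, 40/50 | Power, 13/14 |
|---|---|---|---|
| 5% | 92.15% | 99.9% | 69.8% |
| 10% | 87.3% | 95.4% | 45.4% |
| 15% | 82.45% | 74.7% | 26.7% |

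The class should therefore be chosen deliberately and in advance.

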3.0 STUDY POPULATION

3.1 General Considerations

Subjects will undergo baseline evaluation to determine eligibility for the study. Subjects who do not meet the entry criteria are considered screening failures. Case report forms do not need to be completed for screening failures; however, a record for each patient screened and the reason for screening failure must be indicated in the screening log.

The investigator and/or designated study personnel are responsible for screening all potential candidates and selecting those who are appropriate study candidates as defined by the following inclusion and exclusion criteria.

Signed informed consent will be obtained from the patient before any specific study procedures are undertaken. The patient will sign one original informed consent and a copy will be provided to them. The study requirements should be discussed with the patient with ample time provided for the consent review. All required parties (e.g., patient, witness, investigator or designee) should sign and date on the same consent as the patient.

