1.2 Alternative Treatments and Methods

Patients that have agreed to participate in the study and meet the inclusion criteria and have signed the informed consent form and present on the day of treatment for the endovascular diagnostic procedure will be considered for the study. It is at this point when it will be determined that the patient meets all of the inclusion criteria. If the patient's lesion can be crossed with a guide wire or if the physician feels that other options are more appropriate for the patient, the patient will be treated with the laser catheter and not be included in the study.

There are several commercially available CTO crossing methods and atherectomy systems on the market today. These include standard guide wire manipulation. Standard guide wire recanalization should initially be attempted, even for long, occlusive lesions. Although the inability to remain intraluminal or re-enter the true lumen distally are the main reasons for failure of this technique, there is still a relatively high chance of success. For aortoiliac lesions, an ipsilateral retrograde femoral approach is usually the simplest, but an alternative approach from contra lateral femoral or brachial access may be needed. For superficial femoral artery (SFA) lesions, a contra lateral femoral approach with a crossover sheath is usually needed, but for more distal lesions, such as infrapopliteal, an ante grade femoral approach may be preferable, so that device torquability and push ability is optimized.

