6.6.1 Adverse Events

The number of subjects with at least one adverse event will be tabulated.
 The number of subjects and the number of adverse events will be tabulated by severity and causality and relationship to the treatment procedure.

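### Screening failure is not limited to patients never exposed to the laser, so laser-exposed patients can be left out of the success rate and the safety tables

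*Combined protocol and SAP*

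**What the plan says.** Section 3.1 defines the category by eligibility alone: "Subjects who do not meet the entry criteria are considered screening failures". It then sets the record-keeping: "Case report forms do not need to be completed for screening failures", while a line for each screened patient, with the reason for failure, goes into the screening log. Nothing in 3.1 says that the status has to be assigned before the device is used.

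The decisive criterion in 3.2, repeated in the synopsis, is "Have a lesion that is a chronic total occlusion that cannot be crossed with a standard guidewire", followed by "NOTE: This can only be determined at the time of the procedure".

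Three other places bear on who is lasered and who is counted:

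- Section 1.2, on patients whose lesion a wire can cross or for whom the physician prefers another option: "the patient will be treated with the laser catheter and not be included in the study".
- Section 4.2 step 3 lets the wire be withdrawn if it fails, or if, "at the physician's discretion, angiographic factors determine that a guide wire should not be used". Section 2.2 likewise brings into the objective lesions in which a crossing attempt is judged likely to go subintimal or perforate.
- Section 6.6.1: "The number of subjects with at least one adverse event will be tabulated". Neither 6.6.1 nor the rest of section 6 says which patients make up the effectiveness or the safety population, or at what moment a patient is enrolled.

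**The concern.** This is an open-label, single-arm trial tested against a fixed performance goal of 65%. The operator is present for the eligibility call, the laser attempt and the outcome, and section 11.0 declines third-party determination of success. In such a design the denominator has to be fixed before the outcome is known, or at the latest when the device goes in. Here the label that removes a patient from the data can be given in the same session as the laser attempt, or after it.

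Two results depend on the denominator. The first is the crossing rate and its test at 0.025. The second is safety: 2.2.1 makes the absence of device-related major events an outcome measure, so a single event in an exposed patient without a case report form could change that conclusion.

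**Working it through.** **Can an exposed patient be a screening failure under the current text?**

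1. *Lased at discretion.* Sections 2.2 and 4.2 step 3 allow the laser without a failed wire attempt. Section 3.2 requires a lesion that a wire cannot cross. A patient lased by this route has not been shown to meet 3.2, so 3.1 read literally makes that patient a screening failure.
2. *Section 1.2 as printed.* It describes patients who are lased and not included. A negation may have dropped out. As it stands, the sentence conflicts with 1.5 and 3.2. Correcting it would leave route 1 open.
3. *Documented wire failure before lasing.* This patient meets the guidewire criterion and should count as a failure if the laser does not cross. There is no route out here unless the patient is reclassified later.

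**Does anything bring exposed patients back into an analysis?** The screening log in 3.1 must hold a record and a reason; exposure, crossing result and adverse events are not required. The non-compliance log in 9.3 lists unmet entry criteria but assigns nobody to an analysis. Device accountability in 10.0 can show that a catheter was used, not what happened to the patient. Section 8.1 ties adverse events to a study subject who received the device and does not say whether an exposed screening failure is one.

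**Inputs for the arithmetic** (6.2, 6.3, 6.5): exact one-sided binomial test, level 0.025, null rate 65%, assumed true rate 97%, pass rules 13/14 and 40/50.

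**The plan's own figures.** With P(X ≥ r | n, p) the exact binomial upper tail:

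| Rule | Tail at 65% | Power at 97% | Stated power |
|---|---|---|---|
| 13 of 14 | 0.0205 | 0.9355 | 94% |
| 40 of 50 | 0.0160 | above 0.9999 | 99.99% |

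Both reproduce. Each cut-off is the smallest that keeps the level: 12/14 gives 0.0839 and 39/50 gives 0.0342.

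**Omitted failures at the boundary.** Hold the successes fixed and add back failed crossings that were not recorded. No relabelling fraction is needed:

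| Result | p against 65% |
|---|---|
| 40/50 | 0.0160 |
| 40/51 (one omitted) | 0.0279 |
| 40/52 (two omitted) | 0.0455 |
| 13/14 | 0.0205 |
| 13/15 (one omitted) | 0.0617 |

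One omitted failure reverses a result that sits on either cut-off.

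**Sensitivity to relabelling.** Assume a true rate of 65%, a fraction f of failed crossings logged as screening failures, and no successes logged so. The documents give no f. The apparent rate is q = 0.65 / (0.65 + 0.35 × (1 − f)); for f = 20%, q = 0.65 / 0.93 = 0.699.

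| f | q | P(≥ 40 of 50 retained) |
|---|---|---|
| 0 | 0.650 | 1.6% |
| 10% | 0.674 | 3.6% |
| 20% | 0.699 | 7.7% |
| 30% | 0.726 | 15.6% |

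For 13 of 14 retained, f = 20% gives 4.7% and f = 30% gives 7.1%, against 2.1% at f = 0. If instead 50 patients are lased in total and the exact cut-off is reset for the number retained, f = 10%, 20% and 30% give 4.2%, 8.1% and 14.8%.

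**The case against.** The best defence is that eligibility is ordinarily settled before exposure. Section 3.2 asks for the criteria to be met before entry, the introduction to 4.2 places the wire determination ahead of the laser steps, and 1.5 makes the laser a last resort. A failed laser attempt does not undo a documented wire failure. This stands, and it narrows the point to patients lased at discretion and to later reclassification.

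It can also be said that 2.2 shows discretionary cases were meant to be in the study, and that 9.3 treats an unmet criterion as a protocol departure and not as a reason to erase a patient. Both suggest intent. Neither is a rule about who is analysed, and 2.2 does not amend 3.2.

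On direction, the defence is right. One group named in 1.2 has lesions that a wire can cross. Success is defined in 2.2.1 as getting any endovascular device past the occlusion, so leaving these easier lesions out may lower the observed rate.

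On size, the relabelling table assumes selective loss of failures only. Loss unrelated to outcome gives no bias. At the plan's 97%, 50 patients yield 50 × 0.03 = 1.5 expected failures, and relabelling 20% of them moves the rate only to 0.97 / (0.97 + 0.03 × 0.8) = 97.6%.

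Finally, the case report forms and a log template are not reproduced in the text available, so the log might in practice hold more than 3.1 requires. The point rests on what the protocol requires, not on those forms.

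**Conclusion.** The point holds in limited form. Followed literally, stated rules allow laser-exposed patients to fall outside the crossing rate and the 6.6.1 tables, and no enrolment point, analysis set or log brings them back. The patients concerned are those lased without a failed wire attempt, those reclassified afterwards, and, if 1.2 means what it prints, those it describes.

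A reader might infer more: that failed crossings in general will drop out, that the success rate is biased upward, or that the 0.025 error rate is already broken. The documents support none of these. A patient with a documented wire failure still counts, the direction depends on who is dropped, and the inflated pass probabilities depend on assumed fractions. They show sensitivity and do not estimate a bias.

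Two things need no assumed fraction. Safety data on excluded exposed patients are lost whichever way the rate moves. And a result at the cut-off cannot absorb a single omitted failure: p goes from 0.016 to 0.028 for 40/51, and from 0.021 to 0.062 for 13/15.

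**What to change.** In 3.1, limit screening failure to consented patients in whom the laser catheter was never introduced. Require a case report form for every patient in whom it is introduced. In section 6, count all of these patients in the primary denominator, with not crossed as failure, and in the 6.6.1 tables. Report any entry criterion found unmet as a deviation, and add a supporting analysis restricted to patients who meet 3.2.

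Reconcile 1.2 with 1.5 and 3.2, and 2.2 and 4.2 step 3 with 3.2, on who receives the laser. Which reading is intended is for the sponsor and the investigators to state.

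Sample size, cut-offs and power do not change. The cost is protocol wording and a few more forms. The observed success rate may shift slightly in either direction.
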